3.2 Exclusion Criteria

- **3.2.1** Clinical T4 tumors.
- **3.2.2** Clinical N2 disease estimated as four or more lymph nodes that are ≥ 8 mm.
- **3.2.3** Primary surgeon indicates need for abdominoperineal (APR) at baseline.

3.2.4 Tumor is causing symptomatic bowel obstruction or patients who have had a temporary diverting ostomy are ineligible.

3.2.5 Chemotherapy within 5 years prior to registration. (Hormonal therapy is allowable if the disease free interval is \geq 5 years.)

3.2.6 Any prior pelvic radiation.

3.2.7 Any of the following because this study involves an agent that has known genotoxic, mutagenic and teratogenic effects:

- Pregnant women
- Nursing women
- Men or women of childbearing potential who are unwilling to employ adequate
- contraception

3.2.8 Co-morbid illnesses or other concurrent disease which, in the judgment of the treating investigator obtaining informed consent, would make the patient inappropriate for entry into this study or interfere significantly with the proper assessment of safety and toxicity of the prescribed regimens.

3.2.9 Patients with threatened radial margins, defined as tumors with distance of 1mm or less, or adherent to the mesorectal fascia.

4.0 SCHEDULE OF TESTS

Test & procedures	≤ 28 days pre- registration	≤60 days prior to therapy	Prior to each cycle TASOX, - 3 days ¹	Pre-op visit after completion of cycle 6 TASOX, ie. ≤ 56 days after day 14, cycle 6 ^{8,10,12}	Post- Surgery 2-8 weeks post - op
History and physical	X		X	X	X
Pulse, BP and temperature	X		X	X	x
ECOG			X	X	X
Weight	Χ		X	X	X
Height	Χ				
Adverse Events ¹⁰			X	X	
Hematology ²	Χ		X	X	
Chemistry ³	Χ		X	X	
CEA	Χ		X	X	X
Pregnancy test ⁴	X		X— cycle #1 only		
Pathology confirmation of rectal adenoca.		$\mathbf{x} \leq 90 \text{ days}$			
Rectal exam and proctoscopy ⁵		X			
MRI of pelvis ^{6,8}		X		x ^{11,8}	
CT Chest or chest Xray ^{7,8}		X			
CT of abdomen with contrast ^{7,8}		X			
Documentation of post-operative complications- see					X
Section 6.4.					

1. Recommendations for timing of therapy:

- Radiation must commence within 3 weeks of study registration.
- Chemotherapy with TAS-102 must begin within 1-3 weeks after completion of radiation.

- Patients must have assessment at the time of progressive disease, study withdrawal, or removal.

2. Hematology includes hemoglobin, platelets and absolute neutrophil count (ANC).

3. Chemistry includes SGOT (AST), SGPT (ALT), total bilirubin, creatinine.

4. Urine or serum pregnancy test per institutional standard required for females of childbearing potential \leq 7 days of registration.

5. Rectal exam and proctoscopy are ideally to be performed by the primary surgeon. Proctoscopy should be performed \leq 90 days prior to registration or after registration but before the start of treatment. Proctoscopy may be accomplished using rigid proctoscopy or as part of a flexible sigmoidoscopy or colonoscopy.

6. Pelvic MRI Scan, with or without contrast per treating investigator/institutional standards, is to be performed within 60 days prior to treatment start. Use same imaging modality throughout the study.

7. A PET/CT scan may be performed in lieu of a CT scan with contrast, but a CT scan is preferred.

8. Scans do not have to be performed at the trial site; they can be performed at other locations as long as images are available for review. Scan is to be performed within </= 60 days prior to registration. Contrast is preferred but not required for the CT of the chest. Contrast is required for the CT of the abdomen.

9. Recommendation: Surgery should be performed within 10 weeks AFTER the 6th cycle of neoadjuvant TASOX, and restaging investigations should be obtained within 8 weeks (56 days) AFTER day #14, cycle 6.

10. Adverse Events form to be completed at the start of radiation therapy.

11. Pelvic MRI should be booked within 56 days of completion of cycle #6 of TASOX, i.e. within 1-56 days AFTER day #14, cycle 6.

12. Patients that achieve a complete or near complete Clinical Response (cCR or ncCR) may choose to pursue a course of watch and wait with agreement of their treating surgeon. A thorough discussion is recommended with their surgeon concerning the risks and benefits of watch and wait and both they and their physician agree with the intended approach. Patients that pursue a course of watch and wait remain evaluable on study and will be classified as having a ypT0N0 response for the purposes of the NAR score if they do not proceed to TME surgery within 24 months of completing cycle 6, day 14.

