2.2 Secondary Objective

The secondary objective is to describe the adverse event profile and surgery complications among treated subjects.

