6.4 Surgical Therapy

Standard surgical therapy with a total mesorectal excision (TME) is to be done within 10 weeks of completion of cycle #6 of chemotherapy with TASOX with staging to be done within 8 weeks after day 14 of cycle 6.

Operative approach will be at the discretion of surgeon, and can include either laparoscopic (or robotic-assisted laparoscopic) or open anterior or low anterior resection with or without temporary fecal diversion. Preoperative antibiotics and bowel preparation are institution specific will be at the discretion of the operating surgeon. The mobilization of the proximal colon and splenic flexure may be performed by laparoscopic, laparoscopic-assisted, robotic-assisted or hand-assisted at the discretion of the surgeon to limit the incision to the lower abdomen. The pelvic dissection should include TME, division of inferior mesenteric vascular pedicle, transection of the specimen, and anastomosis. Anastomosis may be stapled or hand-sewn. Variation in technical approaches will be at the surgeon's discretion as they are impacted by the patient's body habitus, incisions, and tumor location.

Patients that achieve a complete or near complete Clinical Response (cCR or cCR), may choose to pursue a course of watch and wait with agreement of their treating surgeon. A thorough discussion is recommended with their surgeon concerning the risks and benefits of watch and wait and both they and their physician agree with the intended approach. Patients that pursue a course of watch and wait remain evaluable on study and will be classified as having a ypT0N0 response for the purposes of the NAR score if they do not proceed to TME surgery within 24 months of completing cycle 6, day 14.

Surgical Complications

Perioperative and postoperative complications will be collected and submitted; see Section 10.0.

Early complications (within 30 days)

Morbidity and mortality will be closely monitored and recorded using the study data forms with the following definitions:

- 1. Pulmonary, urinary tract, and intraabdominal infections will be defined by the need for antibiotic treatment and/or interventional radiology drainage.

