10.0 ADVERSE EVENT (AE) REPORTING AND MONITORING

10.1 Adverse Event Characteristics

CTCAE term (AE description) and grade: The descriptions and grading scales found in the revised NCI Common Terminology Criteria for Adverse Events (CTCAE) version 5.0 will be utilized for AE reporting. All appropriate treatment areas should have access to a copy of the CTCAE version 5.0.

Adverse event monitoring and reporting is a routine part of every clinical trial. First, identify and grade the severity of the event using the CTCAE v5.0. Next, determine whether the event is expected or unexpected and if the adverse event is related to the medical treatment or procedure. With this information, determine whether the adverse event must be reported as an expedited report.

The safety reporting period begins after the subject has signed the informed consent and ends 28 days after the last dose of study drug. It is only required that SAEs be reported following consent and prior to radiation therapy initiation, while all AEs (serious and non-serious) be reported thereafter.

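### Early surgical complications are defined over 30 days, but the only scheduled point for documenting them may fall as early as day 14, leaving up to 16 days without a scheduled assessment

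*Combined protocol and SAP*

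**What the plan says.** Section 2.2 sets one secondary objective, to "describe the adverse event profile and surgery complications among treated subjects". It is descriptive. Section 14 gives no rate, threshold, denominator or test for complications.

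Section 6.4 gives the window under the label "Early complications (within 30 days" and states the duty to record: "Morbidity and mortality will be closely monitored and recorded using the study data forms with the following definitions". It then lists the kinds of complication. The same section says "Perioperative and postoperative complications will be collected and submitted; see Section 10.0".

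In Section 4.0 the row "Documentation of post-operative complications- see" (it continues by pointing to Section 6.4) is marked in one column only, "Post- Surgery 2-8 weeks post - op". The Adverse Events row has no mark in that column. No second post-operative contact, chart review or day-30 cut-off appears.

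Section 10.1 states that the safety reporting period "ends 28 days after the last dose of study drug".

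**The concern.** The endpoint window and the assessment window do not match. A patient documented on day 14 and a patient documented on day 40 both enter the same description of early complications, yet the schedule guarantees 14 days of information for the first and the full 30 for the second. For the first patient, a readmission or death on day 20 lies inside the protocol's own definition, but no scheduled assessment is left at which it would be recorded.

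Provided that events after day 30 are not counted as early, a mismatch of this kind can push the result in one direction only, towards too few complications. How the operation is tolerated after short-course radiation and TASOX is one of the two things the secondary objective asks about. The group is small, so a few events shape the description.

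**Working it through.** The documents state no rate, sample size or power for complications, so there is no figure of the plan to reproduce. The check is calendar arithmetic.

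**1. Gap left by the scheduled visit**

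Inputs: a 30-day window (Section 6.4) and a visit at 2 to 8 weeks, that is, day 14 to day 56 (Section 4.0).

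- Largest gap: 30 − 14 = 16 days, and 16/30 = 53% of the window.
- Permitted visit days: 56 − 14 + 1 = 43. Those before day 30 are days 14 to 29, which is 16 days, and 16/43 = 37%.
- Mean shortfall over those 16 days: (16 + 15 + … + 1)/16 = 136/16 = 8.5 days.
- A visit on days 30 to 56 leaves no gap.

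The 37% is a share of calendar days. It is not a forecast of how many patients will be seen early, since the documents do not say when sites book the visit.

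**2. Whether Section 10 closes the gap**

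Inputs: reporting ends 28 days after the last dose (Section 10.1), TAS-102 is taken on days 1 to 5 of a 14-day cycle (Section 6.2.1), and oxaliplatin is given on day 1 (Section 6.3).

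- Last scheduled dose: cycle 6 day 5. Reporting ends on cycle 6 day 5 + 28 = day 33, which is 33 − 14 = 19 days after cycle 6 day 14.
- If surgery takes place s days after cycle 6 day 14, Section 10 reporting runs to post-operative day 19 − s.

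| Surgery, days after cycle 6 day 14 | Section 10 reporting runs to |
|---|---|
| 0 | post-operative day 19 |
| 5 | post-operative day 14 |
| 28 (limit in Section 6.0) | closed before surgery |
| 70 (limit in Section 4.0 note 9 and Section 6.4) | closed before surgery |

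Section 10 adds something beyond a day-14 visit only if surgery comes less than 5 days after cycle 6 day 14, and even then it does not reach day 30. The 4-week and 10-week surgery limits contradict each other and must be reconciled. The conclusion here is the same under either.

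**3. Scale, by assumption only**

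The documents give neither complication rates nor their timing, and they do not say how many patients will be operated on. Purely for illustration, assume 24 operated patients, a complication rate p of 10% to 30%, a share f of 10% to 30% of complications first appearing after day 14, every visit on day 14, and no later capture at all. The expected number missed is 24 × p × f:

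- low end: 24 × 0.10 × 0.10 = 0.24;
- high end: 24 × 0.30 × 0.30 = 2.16.

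If only half the visits fell on day 14 and the rest on or after day 30, this would halve to about 0.1 to 1.1. One event in 24 patients is 1/24 = 4.2 percentage points; in 27, the planned enrolment, it is 1/27 = 3.7.

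**The case against.** The best reply is that Section 6.4 carries its own obligation. The schedule row points to that section, and its instruction to monitor and record morbidity and mortality sits under the 30-day label and is not tied to a visit. A site that stopped recording at day 14 would meet the visit window but not Section 6.4. Most of the listed complications are also defined by an intervention or extra care, such as antibiotics, drainage, transfusion, reoperation or a longer stay, so they leave a trace in the medical record. Section 15.0 adds regular review of patient updates and outcomes.

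This stands as far as it goes. A reader might infer from the schedule that days 15 to 30 go unobserved and that the reported rate is bound to be too low. The documents do not support that: those days lack a scheduled assessment, which is a narrower statement, and loss requires an early visit, a later event, and a failure to pick it up under Section 6.4.

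A reader might also take 24 as the number of operations. In Section 14.2 it is the number required for the NAR comparison. Patients on watch and wait stay evaluable for NAR without surgery unless they later proceed to it, so the number operated is unknown.

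What the reply does not supply is a method. Section 6.4 names no time point, contact or cut-off by which day-30 status is to be established, and the section it refers to for reporting will usually have closed. Capture of later events is left to local practice.

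**Conclusion.** The point holds as a mismatch between the defined window and the scheduled assessment. The shortfall is at most 16 of 30 days, occurs only for visits on days 14 to 29, and is not made good by Section 10. The Section 10 result assumes on-schedule cycle 6 dosing. Follow-up can differ between patients, and the complication count can be too low. By how much cannot be computed from the documents; the range of about 0.2 to 2.2 missed events rests wholly on assumed inputs and the worst-case visit day.

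The reach is limited. A reader might infer that the secondary objective as a whole is compromised, but adverse events on treatment are assessed before each TASOX cycle and at the pre-operative visit, so only the surgical part is exposed. That part is descriptive and untested, and the primary NAR analysis and the sample size are unaffected. This is an inexpensive improvement worth making, not a flaw that threatens the trial.

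**What to change.** Require the complications form to be completed or updated through post-operative day 30 or death, in one of two ways:

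- set that assessment at days 30 to 56, inside the existing 8-week limit; or
- keep the 2-to-8-week visit and add a day-30 chart check or telephone call for patients documented earlier.

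Record onset dates, so that events after day 30 are not counted as early. Align Sections 4.0, 6.4 and 10.1, so that the reference from Section 6.4 leads to a reporting period that covers the 30 days after surgery.

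For reporting, use all operated patients as the denominator, count every observed event, and state how many patients had ascertainment through day 30. Do not restrict the rate to patients followed to day 30: that would drop, for example, a patient with a documented day-5 complication whose last contact was on day 20.

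Either option brings the longest stretch without a scheduled assessment from 16 days to 0. The cost is an edit to the schedule, a sentence each in Sections 6.4 and 10.1, and one chart check or call for some operated patients. If the visit itself is moved instead, the history, examination and vital signs marked in the same column move with it, so the added check disturbs the schedule less.

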5.0 REGISTRATION PROCEDURES

To be completed after eligibility determination and at least 24 hours prior to first day of radiation therapy. It will be done by completing the registration form and emailing the following information to [contact].

All the following information will be required:

- Name of institution.
- Patient initials.

- Age.
- Sex.
- Race.
- Date of diagnosis.
- Informed consent signed date.
- Projected treatment start date. i.e., start date of radiation therapy.

6.0 PROTOCOL TREATMENT

Therapy: Study schema is summarized in Section 2.3. Patients are initially treated with 25 Gy in five fractions of 5 Gy conformal pelvic radiation. Radiation is to be started within 3 weeks of registration. TASOX should be commenced within 3 weeks of radiation completion. Patients are treated with 6 x 14 day cycles of TASOX. Within 4 weeks of the end of cycle #6 of TASOX patients undergo re-staging. Surgery should be performed within 4 weeks AFTER day 14, cycle#6 of TASOX, i.e., 28 days after day 14, cycle 6.

6.1 Radiation Therapy

[figure not shown]
CT Simulation Techniques

Prone position with use of a bowel displacement device 'belly board' is recommended and may be particularly advantageous for patients with a larger body habitus to improve small bowel sparing (**Figure 2**). At the time of simulation, placement of a radiopaque anal marker may be useful to determine the distance of the disease from the verge for contouring purposes. For males, it is important to pull the external genitalia center and downward. Oral contrast is recommended to be given approximately 30 minutes prior to simulation for better small bowel visualization. If oral contrast is used, the contrast needs to be overwritten to a normal density or planning needs to occur on a pre-contrast scan. Intravenous contrast may be useful in visualizing and contouring the elective nodal vessels, particularly in patients who are thin; however, more commonly, fusion with the patient's CT with contrast staging study is used. For additional small bowel sparing, 16-20 oz of water should be administered PO 30 minutes before the CT for bladder filling,but remember to reproduce the same filling prior to each treatment. Additionally, it is important for the patient to maintain good regular bowel function in order to keep the rectum empty. Once the patient is appropriately positioned, CT images at 2-3 mm intervals from the upper lumbar spine to the mid-femur should be obtained.

Figure 2: Prone CT simulation using a belly board. Blue arrow delineates the gap in the prone belly board that allows for geometric displacement of small bowel. Yellow arrow shows that bladder filling may provide additional small bowel displacement.

Target Volumes

According to the International Commission on Radiological Units 50 guidelines, all target and normal tissue structures are contoured on the planning CT slices. Multiple consensus atlases now exist from the RTOG (18), Australasian Gastrointestinal Trial Group (19) and the EORTC (20) that illustrate target definitions with representative case examples. RTOG also has a pelvic normal tissue contouring atlas (21). When contouring the GTV, one should use all available clinical and radiographic information (digital rectal exam, endoscopy, pelvic MRI, and other imaging as available) including anal verge markers at the time of simulation. Include all macroscopic tumor in the GTV (primary, nodal GTV adjacent to the rectal wall and extramural vascular invasion) on each CT slice and any adjacent normal rectal wall on the same slice. Contouring of the GTV may be aided by registration of the diagnostic MRI (and/or pelvic CT with contrast and/or PET if available) in the treatment planning system. Other large nodal (> 1 cm) disease that either shows increased uptake on PET or has abnormal architecture on CT may also be included in the GTV.

Construction of the clinical target volume (CTV) of the primary tumor (CTV_2500) is performed by an isotropic expansion of 1.0 cm from the GTV. The CTV_2500 should include the entire GTV. This structure should be modified to account for the natural barriers of bone and muscle if the tumor does not involve these structures.

An elective nodal dose volume (CTV_2000) should be constructed that includes the CTV_2500 and all elective nodal CTVs. Elective nodal CTVs include the entire mesorectum, internal iliac, and presacral lymph node regions. The CTV_2000 superior limit should be the more superior of 1 cm above the most superior limit of GTV, or the L5/S1 interspace. This structure should be modified to account for the natural barriers of bone and muscle if tumor does not involve these structures. Common errors in contouring the elective nodal volume include failure to correctly contour the entire extent of the mesorectum. When contouring the CTV_2000 internal iliac lymph node region, a 7 mm isotropic expansion around the vessels should be performed. When contouring the CTV_2000 presacral lymph node region, a 10 mm expansion in front of the sacrum should be performed.

PTV_2500 and PTV_2000 are then constructed by placing a 5 mm isotropic expansion around the CTVs. If daily IGRT cannot be used (kV kV match or CBCT) or if 3-D planning is performed, PTVs should be developed using a 10 mm expansion around the CTVs. In contouring of the normal pelvic organs at risk (OARs), the small bowel, left femoral head, right femoral head, genitalia, bladder, pelvic bones, large bowel, and skin should all be outlined on each axial CT slice. The external contours of all pelvic bones, including iliacs, lumbosacral spine and lower pelvic bones, should be contoured together as a surrogate for pelvic bone marrow. Bowel should be drawn as individual loops without the intertwining mesentery from L3 down. The tissue within the skin surface and outside all other critical normal structures and PTVs is designated as unspecified tissue. Excellent definitions of normal pelvic organs may be found in the RTOG atlas (Gay 2012). A representative IMRT plan and radiation targets are shown in **Figure 3**.

Although IMRT is preferred, if 3-D is performed, one can perform sequential plans (i.e. initial PTV_2000 over four days followed by a single boost fraction).

[figure not shown]

Figure 3. High dose distribution of 3D-CRT vs IMRT planning. This is a patient for whom prone positioning on belly board device did not displace bowel. Sagittal (A and C) and axial (B and D) views of 3D-CRT (A and B) and IMRT (C and D) plans are presented. The IMRT plan demonstrates reduction in high dose region to bowel and bladder. Dose color wash reflects 2000 cGy in blue and 2500 cGy in red.

Dosimetric Planning and Delivery

Conformal radiation with IMRT is preferred using 6MV photon energy and either static field or VMAT, but 3-dimensional 6-18MV photon treatment will be allowed. Proton therapy is not allowed. When using VMAT, consider 270 degree arc fields to avoid a field directly entering the genitalia. IMRT is preferred as planning allows for differential doses to the gross disease, elective nodal regions and the OARs. The OARs used in optimization typically include the small bowel, femoral heads, genitalia, bladder, pelvic bones, and large bowel. In addition, when performing IMRT, all PTVs should spare non-target skin surfaces manually or automatically trimmed by 3-5 mm (unless there is skin involvement). For bone marrow sparing, pelvic bones including the iliac crests, lumbosacral spine, and lower pelvic bones should be contoured

together as a surrogate for pelvic bone marrow. Representative target dose coverage and normal tissue constraints are outlined in **Table 2 and Table 3**.

Treatment planning priorities should be considered in order of decreasing importance:

- 1. PTV 2500
- 3. PTV²⁰⁰⁰
- 4. Small bowel
- 5. Femoral heads
- 6. Bladder
- 7. Large bowel

Of note, pelvic bone marrow and genitalia should be kept as low as possible. However, we do not have standard five fraction constraints for these organs.

Table 2. Target Dose and Coverage Parameters

			Max Point Dose
Target	Coverage	Total Dose	(Gy)
	100% of		
	the		
	volume to		
	100% of		110% to be within
GTV	the dose	25 Gy	GTV
	98% of		
	the		
	volume to		
	100% of		110% to be within
CTV_2500	the dose	25 Gy	GTV
	95% of		
	the		
	volume to		
	95% of		110% to be within
PTV_2500	the dose	25 Gy	GTV
	98% of		
	the		
	volume to		
	100% of		
CTV_2000	the dose	20 Gy	110%
	95% of		
	the		
	volume to		
	98% of		
PTV_2000	the dose	20 Gy	105%

Table 3. Normal Organs at Risk Treatment Planning Parameters for Rectal Cancer

Organ at Risk	Suggested Constraints
Small Bowel	V20 < 50cc
	max point dose 25 Gy
Femoral Head (L)	V20 < 10%
Femoral Head (R)	V20 < 10%
Large Bowel	V20 < 50cc
	max point dose 27 Gy
Bladder	V20 < 50cc
	max point dose 27 Gy
Large Bowel	V20 < 50cc
	max point dose 27 Gy

For IMRT plans, patient specific quality assurance (QA) is highly recommended. QA is performed by delivering the plan onto a phantom or portal imager to measure the 2D/3D dose. Measured dose distribution will be compared to planned dose distribution using a Gamma criterion of 4% dose difference and 3 mm distance to agreement. The pass rate should be at least 90% measured for the entire plan.

Image-guided radiation therapy (IGRT): Patients should receive daily KV images for set up and treatment verification. Bone should be used as the surrogate. Corrections should be made for shifts of 3 mm or greater and recorded. Daily cone beam CT images (CBCTs), if available, may also be helpful and strongly recommended to evaluate the relationship of the CTV to the bladder/rectum and to verify male genitalia position.

For IMRT systems where the isocenter is not defined (e.g., tomotherapy), setup verification images may consist of a series of axial CT images (megavoltage or kilovoltage) obtained over at least 5 cm length, to be compared with simulation CT images. It is recommended that there be an option to display target structures on the simulation images. It is also recommended that the setup verification images be obtained at levels where cephalocaudad positioning, as well as transverse positioning, can be verified. Appropriate levels would include either around the mid to upper sacrum or around the upper border of the acetabulae.

Daily doses: PTV_2500 will receive 500 cGy daily x five fractions for a total of 2500 cGy to the gross cancer PTV over 5-7 days. Fractions should be consecutive but may be spread out over two weeks (i.e. over the weekend). The CTV_2000 will simultaneously receive 400 cGy daily x five fractions for a total of 2000 cGy to the elective nodal disease. While IMRT is strongly preferred, 3-D planning with a sequential approach (PTV_2000 over four consecutive fractions followed by the PTV_2500 volume in one treatment as a boost of 500 cGy to the gross cancer PTV) is

allowed. There should be no treatment break. If a treatment break of more than 3 days is needed, please contact the study PI. No bolus should be used.

